12.2. Processing and Handling of Pharmacokinetic Samples

Whole blood will be collected at each scheduled sample timepoint. Detailed procedures for the collection of blood samples including further processing into plasma will be provided in a separate laboratory manual. The storage and shipment procedures for subsequent bioanalysis, will be provided to the investigational site and home health care company in a separate document before the study is initiated.

12.3. Bioanalysis

Plasma concentrations of OCA and its conjugates, glyco-OCA and tauro-OCA, and metabolite OCA glucuronide will be determined using a validated liquid-chromatography mass spectrometry/mass spectrometry (LC/MS/MS) method. A detailed description of validation information and results from the bioanalytical assay will be provided in separate reports. These samples may be used for evaluation of metabolites of OCA or other concomitant medication, for further evaluation of the bioanalytical method, and for analyses that provide information on the metabolic pathways used or impacted by OCA.

13. ASSESSMENT OF SAFETY

13.1. Adverse Events and Serious Adverse Events

13.1.1. Definitions of Adverse Events

13.1.1.1. Adverse Event

AEs are defined as any untoward medical occurrence associated with the use of the investigational product in humans, whether or not considered related to investigational product. An AE, also referred to as an adverse experience, can be any unfavorable and unintended sign (eg, an abnormal laboratory finding), symptom, or disease temporally associated with any use of the investigational product, without any judgment about causality and irrespective of route of administration, formulation, or dose, including an overdose.

AEs include, but are not limited to: (1) a worsening or change in nature, severity, or frequency of condition(s) present at the start of the study; (2) patient deterioration due to primary illness; (3) intercurrent illness; and (4) drug interaction. For reporting purposes, pregnancy is not considered an AE.

Patients should be questioned about AEs in a general way, without leading the patient or asking about the occurrence of any specific symptom. The Investigator should attempt to establish a diagnosis of the event based on signs, symptoms, and/or other clinical information. The diagnosis and not the individual signs/symptoms should be documented as the AE. For example, if the underlying disease process is a stroke, it would not be appropriate to record the AE by describing the symptoms “sudden numbness, dizziness, and difficulty speaking.” The AE medical term of “stroke or cerebrovascular accident” should be recorded as it more accurately describes the AE.

13.1.1.2. Serious Adverse Event

An AE is considered “serious” if, in the view of either the Investigator or Sponsor, it results in any of the following outcomes:

- Death
- Is immediately life threatening
- Requires in-patient hospitalization or prolongation of existing hospitalization
- Results in persistent or significant disability or incapacity
- Results in a congenital abnormality or birth defect
- Is an important medical event that may jeopardize the patient or may require medical intervention to prevent one of the outcomes listed above.

Events **not** considered to be SAEs are hospitalizations for:

- Routine monitoring of the studied indication and not associated with any deterioration in condition or AE;
- Elective treatment for a pre-existing condition that did not worsen;
- Respite care or observation when there is no AE associated with the hospitalization.

13.1.1.3. Treatment-Emergent Adverse Event

A treatment-emergent AE (TEAE) is any event not present before the initiation of the investigational product or any event already present that worsens in either intensity or frequency following exposure to the investigational product.

13.1.2. Relationship to Investigational Product

The Investigator will document her/his opinion of the relationship of the AE to treatment with the investigational product using the criteria outlined in Table 7. An AE for which there is a “reasonable possibility” that the investigational product caused the AE is otherwise referred to as suspected adverse reaction (SAR). “Reasonable possibility” means there is evidence to suggest a causal relationship between the investigational product and the AE.

If the relationship between the AE/SAE and the investigational product is determined to be “definite,” “probable,” or “possible” the event will be considered to be related to the investigational product for the purposes of expedited regulatory reporting.

Table 7: Relationship of Adverse Events to Investigational Product

Relationship	Description
Definite	A reaction that follows a reasonable temporal sequence from administration of the investigational product or in which the investigational product level has been established in body fluids or tissue; that follows a known or expected response pattern to the suspected investigational product; and that is confirmed by improvement on stopping or reducing the dosage of the investigational product, and reappearance of the reaction on repeated exposure.
Probable	A reaction that follows a reasonable temporal sequence from administration of the investigational product; that follows a known or expected response pattern to the suspected investigational product; that is confirmed by stopping or reducing the dosage of the investigational product; and that could not be reasonably explained by the known characteristics of the patient’s clinical state.
Possible	A reaction that follows a reasonable temporal sequence from administration of the investigational product; that follows a known or expected response pattern to the suspected investigational product; but that could readily be produced by a number of other factors.
Unlikely	An event that does not follow a reasonable temporal sequence from administration of the investigational product; that does not follow a known or suspected response pattern to the suspected investigational product; and that could reasonably be explained by known characteristics of the patient’s clinical state.
Not Related	Any event that does not meet the above criteria.

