5.4. Rationale for Study Design and Dose for Investigational Product

5.4.1. Rationale for Study Design

There are limited clinical data available to support the use of OCA in patients with PBC with moderate to severe hepatic impairment. The current recommended dosing of such patients is

based on modeled systemic and hepatic concentrations. Therefore, Study 747-401 is specifically designed to characterize the PK, safety, and efficacy of OCA in this patient population.

PK and safety parameters will be evaluated as the primary objectives and efficacy parameters will be evaluated as secondary and additional objectives. While the prognostic utility of ALP has been established by the Global PBC study group, increasing levels of bilirubin are more relevant to understanding the progression of end stage liver disease. Consistently, bilirubin is a key marker of advancing disease as characterized by the Global PBC study group as well as its incorporation into model of end stage liver disease (MELD), Child-Pugh (CP), and Mayo risk scores. As such, the potential of OCA to stabilize bilirubin levels will be evaluated.

In order to generate data for the patient population in a timely fashion, Study 747-401 is designed with a relatively short-term, 1-year double-blind treatment period to gather primarily PK and safety data. Therefore, the study will not formally test the long-term efficacy of OCA on clinical outcomes.

Although Study 747-401 is not designed to formally evaluate clinical outcomes, these data will be collected and assessed as an additional objective. Given the importance of evaluating clinical outcomes in patients with the most advanced form of the disease, these events will be prospectively adjudicated consistent with the procedures implemented in ongoing PBC studies. This will allow for a more robust meta-evaluation of clinical outcomes in patients with moderate to severe hepatic impairment following the completion of both studies.

Study 747-302 is specifically designed to confirm clinical benefit across the spectrum of disease including patients with hepatic impairment. Data collected from Study 747-401 will serve as a bridge to the 747-302 study.

Taken together, data from this study will complement the data from Study 747-302 and offer the opportunity to better inform the benefit risk profile and appropriate treatment of hepatically-impaired patients.

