9.4.3. Emergency Unblinding Procedures

Treatment assignment for individual patients will be made available to the Investigator for medical emergency use only (such as unblinding which is necessary in order to treat an serious adverse event [SAE] through the IWRS system). When possible, the Medical Monitor should be consulted in the event that a medical emergency necessitates unblinding (ie, in situations where knowledge of the blinded treatment assignment is necessary for further medical management of the patient). If it is not reasonable to inform the Medical Monitor in advance of the unblinding, the Investigator must promptly document in the patient's record the rationale for unblinding and should subsequently contact the Medical Monitor to explain any premature unblinding of treatment assignment. Procedures for unblinding a patient's treatment will be provided separately to the Investigator. Similarly, if the Medical Monitor breaks the blind for an individual patient for the purpose of evaluating an emergent safety issue, the Medical Monitor will document within study documentation the rationale, circumstances, and the person or persons being informed about the unblinding.

The DMC will have access to the IWRS and will be able to unblind individual patients. Refer to [Section 15.8](#) for further details regarding DMC access to blinded and unblinded data. The DMC will document details about any unblinded patient data reviews in the closed session DMC minutes, which will be made available to the Sponsor only after the database is locked and the study is unblinded. Cases of premature unblinding, as noted above, will also be reviewed by the DMC.

Access to treatment assignments will also be made available to the designated Intercept staff responsible for expedited safety reporting of suspected unexpected serious adverse reactions (SUSARs) to the Regulatory Authorities.

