15.4.1. Adverse Events

AEs will be coded using MedDRA. Summary tables of TEAEs will be provided.

Each AE summary will be displayed by treatment group. Summaries that are displayed by SOC and PT will be ordered by descending order of incidence of system organ class and preferred term within each system organ class. Summaries of the following types will be presented:

- Overall summary of TEAEs.
- Patient incidence of TEAEs and the total number of entries by MedDRA SOC and PT. This summary will be repeated for all subgroups.
- Patient incidence of TEAEs by MedDRA SOC, PT, and highest severity. At each level of patient summarization, a patient is classified according to the highest severity if the patient reported 1 or more events. AEs with missing severity will be considered severe for this summary.
- Patient incidence of TEAEs by MedDRA SOC, PT, and closest relationship to investigational product (Related/Not Related). Related AEs are those with relationships reported as “Definite,” “Probable,” or “Possible,” and unrelated AEs are those with relationships reported as “Unlikely” or “Not Related.” At each level of

patient summarization, a patient is classified according to the closest relationship if the patient reported 1 or more events. AEs with a missing relationship will be considered related for this summary.

- Patient incidence of serious TEAEs and the total number of entries by MedDRA SOC and PT.
- Patient incidence of TEAEs leading to investigational product withdrawal or study discontinuation by MedDRA SOC and PT. This is a subset of the AEs where Action Taken with Study Treatment is checked as “Drug Withdrawn” or where “Patient Discontinued from Study” is checked.

The following listings will be presented by treatment group and patient:

- All adverse events.
- Serious adverse events (This is a subset of the AEs where serious is marked as “Yes”).
- Severe adverse events (This is a subset of AEs where severity is marked as “Severe”).
- Related adverse events (This is a subset of the AEs where relationship marked as “Definite,” “Probable,” or “Possible”).
- Adverse events leading to Study Drug Withdrawal or Study Discontinuation (This is a subset of the AEs where Action Taken with Study Treatment is checked as “Drug Withdrawn” or where “Patient Discontinued from Study” is checked).
- Adverse events leading to death (This is a subset of the AEs where the corresponding AE number is specified on the Death eCRF).

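### Table 7 requires a known or expected pattern for every related category and makes Not Related the residual class, so read literally a novel reaction is recorded as unrelated

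*Protocol*

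**What the plan says.** In the current protocol (Version 2), Section 13.1.2 asks for the Investigator's opinion on relationship "using the criteria outlined in Table 7". Besides a reasonable temporal sequence (or, for Definite only, a measured drug level in its place), the rows require:

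- Definite: a reaction "that follows a known or expected response pattern to the suspected investigational product; and that is confirmed by improvement on stopping or reducing the dosage", plus recurrence on re-exposure.
- Probable: a reaction "that follows a known or expected response pattern to the suspected investigational product; that is confirmed by stopping or reducing the dosage", and not reasonably explained by the patient's clinical state.
- Possible: a reaction "that follows a known or expected response pattern to the suspected investigational product; but that could readily be produced by a number of other factors", with no dechallenge asked for.
- Unlikely: no reasonable temporal sequence, no known or suspected pattern, and an explanation in the clinical state.
- Not Related: "Any event that does not meet the above criteria".

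The paragraph above the table calls an event a suspected adverse reaction when there is a reasonable possibility of causation, explained as evidence pointing to a causal link. It sets no pattern condition. Definite, Probable and Possible count as related for expedited reporting. Section 15.4.1 ("Related AEs are those with relationships reported as") uses the same three grades for the related-TEAE summary and the related-AE listing. Section 13.1.8 uses them, alongside clinical significance, to decide which AEs still ongoing at the final visit must be followed further.

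**The concern.** Safety compared with placebo is a primary objective (Section 6.1), and Section 5.4.1 gives the reason: "There are limited clinical data available to support the use of OCA in patients with PBC with moderate to severe hepatic impairment". In such a population a reaction not yet associated with OCA is a realistic possibility. A causality scale that admits an event as related only when it matches what is already known or expected cannot record such a reaction as related, however strong the evidence in the individual patient.

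The default is also at odds with Section 15.4.1, which counts an AE with a missing relationship as related. Table 7 sends an event that fits no row to the unrelated side. An analysis plan cannot undo this, because the grade is fixed when the Investigator records it.

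**Working it through.** No stated figure is involved, so the check sets the rows side by side and reads them as a rule.

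| Grade | Timing | Known or expected pattern | Dechallenge | Rechallenge | Other explanation |
|---|---|---|---|---|---|
| Definite | required, or drug level found | required | required | required | not mentioned |
| Probable | required | required | required | not mentioned | not explained by clinical state |
| Possible | required | required | not mentioned | not mentioned | other factors could readily produce it |
| Unlikely | must be absent | must be absent | not mentioned | not mentioned | explained by clinical state |
| Not Related | everything else | | | | |

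**Case 1.** New reaction, right timing, positive dechallenge and rechallenge, no other cause. The pattern condition excludes Definite, Probable and Possible. The timing excludes Unlikely. Not Related remains.

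**Case 2.** Known pattern, right timing, patient stays on product, no other cause. Definite and Probable fail for lack of dechallenge, Possible fails because no other factor could readily produce the event, and Unlikely fails on timing. The result is Not Related. Add an alternative cause and the event becomes Possible, so weaker evidence for the drug gives a higher grade.

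**Enumeration.** Take seven yes/no elements: timing, drug level, pattern, dechallenge, rechallenge, explained by clinical state, other factors could produce it. That gives 2^7 = 128 combinations, with the rows applied in table order.

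- All combinations: Definite 12, Probable 4, Possible 10, Unlikely 16, Not Related 86 (sum 128). Related: 12 + 4 + 10 = 26.
- Pattern absent (64): Not Related 48, Unlikely 16, related 0. All 26 related combinations therefore have the pattern.
- Pattern absent, timing present (32): Not Related 32.
- Pattern absent, timing, dechallenge and rechallenge present (8): Not Related 8.

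**Removing only the pattern requirement.** The last 8 all become Definite. Of the 32 with timing and no pattern, 8 become Definite, 4 Probable and 10 Possible, so 22 are related and 32 − 22 = 10 stay Not Related. In all 10, no other factor could readily produce the event: 8 have no dechallenge, and 2 have dechallenge but are explained by the clinical state. This is the Case 2 gap, so the wording of Possible has to change as well.

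**The case against.** Several points on the other side have weight.

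- The table says known or expected. A reaction predictable from OCA's pharmacology qualifies even if never seen before. This stands; the point is confined to reactions outside any known or expected pattern.
- The Investigator gives an opinion, and the reasonable-possibility sentence stands just above the table, so some will grade by that standard. True, but the section still holds two rules that give opposite answers, and grading will differ between Investigators.
- A reader might infer that the Investigator's input to "expedited safety reporting of suspected unexpected serious adverse reactions" (Section 9.4.3) is nil for every unexpected event. The documents do not support that. Section 9.4.3 does not equate unexpected with outside an expected response pattern, and an event absent from the Investigator's Brochure can still fit an expected pattern. Section 13.1.4.2 also has the Sponsor assess causality of each SAE separately.
- A reader might infer that the trial could not detect a new toxicity. That does not follow either. All AEs are recorded whatever the attribution (13.1.4.1), TEAEs and serious TEAEs are tabulated by arm without a relatedness filter (15.4.1), and the DMC meets about quarterly and sees arm-separated tables and SAE narratives (15.8).
- For liver chemistry, 8.4.1.2 has its own attribution rule: significant elevations that resolve on interruption with no other cause found are taken as related. Its closing text sends all hepatic injury events to adjudication whatever their relationship. This covers the central risk, though not other organ systems.
- Case 2 depends on reading the last clause of Possible as an entry condition. Read as a concession, the gap closes. In Child-Pugh B or C cirrhosis another factor will often exist, so Case 2 is the narrower of the two gaps.

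**Conclusion.** The defect is real on the literal wording and is a contradiction within Section 13.1.2. A reaction outside any known or expected pattern that follows dosing cannot be graded as related, whatever the dechallenge and rechallenge evidence, and a known-pattern event can lose its related grade for want of an alternative cause. The related-TEAE summary and related-AE listing are biased towards too few related events, as is the Investigator's causality input. The Sponsor's causality assessment is stated for SAEs and does not change the category reported for 15.4.1.

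The enumeration (0 of 64 without the pattern, 32 of 32 Not Related when timing is present) shows that the exclusion is complete in logic. It is not a probability: the combinations are not equally likely and some are clinically implausible. The documents give no frequency for novel reactions, so the number of events affected cannot be stated. Because the randomised comparison of all TEAEs is intact, this should be corrected but does not endanger the primary safety comparison. The conclusion assumes that each row's elements are cumulative and that Investigators apply the table as written.

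**What to change.** In Table 7:

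- Make the known or expected pattern supportive rather than required for Definite, Probable and Possible.
- Let Possible cover any event with a reasonable temporal sequence and a reasonable possibility of causation that does not meet Probable or Definite. This brings the table into line with the paragraph above it and closes both gaps.
- Define Not Related positively: no plausible temporal sequence, or clear evidence of another cause.

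Do not send every event that fits no row to Possible. That would class as related even events with no temporal sequence to dosing.

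The cost is the wording of one table and the matching eCRF completion guideline. Somewhat more events will be classed as related, in both blinded arms.

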13.1.3. Recording Adverse Event Severity

AEs must be graded for severity (ie, intensity). A severity category of mild, moderate, or severe, as defined in Table 8, must be entered on the AE eCRF. It should be noted that the term “severe” used to grade intensity is not synonymous with the term “serious.” The assessment of severity is made regardless of investigational product relationship or of the seriousness of the AE.

Table 8: Severity of Adverse Events

Grade	Clinical Description of Severity
1 = Mild	Causing no limitation of usual activities; the patient may experience slight discomfort.
2 = Moderate	Causing some limitation of usual activities; the patient may experience annoying discomfort.
3 = Severe	Causing inability to carry out usual activities; the patient may experience intolerable discomfort or pain.

13.1.4. Reporting of Adverse Events and Serious Adverse Events

13.1.4.1. Reporting of Adverse Events

AE data will be collected from the time that signed informed consent is obtained until the patient fully completes her/his study participation of the study.

All AEs, whether believed by the Investigator to be related or unrelated to the investigational product, must be documented in the patient's medical records, in accordance with the Investigator's normal clinical practice and on the AE eCRF. Each AE is to be evaluated for duration, intensity, frequency, seriousness, outcome, other actions taken, and relationship to the investigational product. Redacted medical record source documentation will be requested for all SAEs and emergency room visits.

13.1.4.2. Reporting of Serious Adverse Events

In agreeing to the provisions of this protocol, the Investigator accepts all legal responsibilities for immediate reporting of SAEs to the Sponsor. Immediate reporting implies within 24 hours of becoming aware of the occurrence of an SAE.

All SAEs must be reported to the Sponsor (including suspected liver-related clinical outcome events that qualify as serious). SAEs are reported by entering the SAE data into the study specific EDC system. Entering the SAE data into the EDC system will automatically notify the Sponsor of the event. In the event that the EDC system is inaccessible, an SAE may be reported by:

- E-mail to the SAE email address: PPD [REDACTED]
- Fax using a paper SAE report form: PPD [REDACTED]

If an SAE is reported by fax, an SAE Report form must also be completed in the EDC system as soon as the EDC system is accessible. At a minimum, the following information should be provided at the time of the initial report:

- Patient number
- Event term
- At least 1 criterion classifying the event as serious
- Name and title of the reporting individual
- Causal relationship to the investigational product

The Investigator will assess whether the event is causally related to the investigational product. The Sponsor will also assess whether the event is causally related to the investigational product, in addition to assessing the overall safety profile of the investigational product. The Sponsor will notify the appropriate regulatory agencies as well as all participating Investigators of Safety Reports/Expedited Safety Reports that occur during the study within the time frames required by each regulatory agency.

Following the initial report, any additional information obtained by the Investigator about the SAE must be reported promptly to the Sponsor in the same manner as described above for the initial SAE report. Any supporting source documentation should be faxed to PPD or emailed to PPD as soon as possible.

The Investigator is responsible for submitting information on Safety Reports/Expedited Safety Reports received from the Sponsor to her/his local IRB/IEC, as directed by the local country requirements. Documentation of the submissions to IRBs/IEC s must be retained in the appropriate study file(s). As instructed by the Sponsor, Safety Reports/Expedited Safety Reports should be retained in the appropriate investigative site study files or with the IB.

